“Early Sodium Intake in Preterm Newborns; Randomized Clinical Trial”

NCT04035564

January 2018

Introduction

Hyponatremia is a common complication among preterm infants, renal losses of sodium contribute to the development of hyponatremia in preterm newborns. Sodium imbalances impact in newborns outcome. There is controversy about the time of initiation and the requirements of sodium in premature infants. Hypothesis: early (24 hours of life) sodium supplementation (5mEq/kg/day) prevents the develop of hyponatremia in preterm infants.

This study is a randomized controlled trial in infants less than 35 weeks gestation admitted to the Newborn Intensive Care Unit at Children Hospital in Saltillo Coahuila Mexico.

Infants receive at 24 hours of life; sodium (5mEq/kg/day) versus less than 1mEq/kg/day. Weight, serum and urine sodium, serum chloride, serum and urine creatinine, serum chloride, bicarbonate and glucose are monitored daily during the first 3 days of life. Patients are assessed for hyponatremia, hypernatremia, weight change, sepsis, necrotizing enterocolitis and intraventricular hemorrhage.

Objectives:

1. Compare the risk of hyponatremia in the first 72hrs of life, in preterm newborns with early sodium intake and late sodium intake.
2. Compare the risk of hypernatremia in the first 72hrs of life, in preterm newborns with early sodium intake and late sodium intake.
3. Assess the change in serum sodium in preterm newborns with early sodium intake and late sodium intake.
4. Assess the weight change in preterm newborns with early sodium intake and late sodium intake.
5. Assess the development of complications (sepsis, necrotizing enterocolitis, intraventricular hemorrhage, mortality) in preterm newborns with early sodium intake and late sodium intake.

Study design and statistical analysis

This study is a randomized controlled trial.

Eligibility criteria:

Preterm infants <35 weeks of gestation.

Less than 24 hours of life.

Exclusion criteria:

Urinary malformations
Congenital abdominal wall defect
Intestinal atresia / obstruction
Congenital heart defect

The eligible patients will be simple randomized in two groups:

1. Comparison: Sodium administration, enteral and/or parenteral less than 1mEq/kg/day starting on day of life one.
2. Intervention: Sodium administration, enteral and/or parenteral of 5mEq/kg/day starting on day of life one.

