At admission, gestational age and sex and birth weight will be recorded. Weight will be evaluated every 24 hours for 3 days.

Blood samples will be taken every 24 hours for 3 days to assess serum sodium, creatinine, glucose, sodium bicarbonate and serum chloride levels.

Urine samples will be taken every 24 hours for 3 days to assess urine sodium and urine creatinine levels.

The incidence of hyponatremia, hypernatremia, change of serum sodium and weight change will be evaluated and compared between groups during this time frame (72hrs).

The patients will be following through hospital stay to record the development of sepsis, necrotizing enterocolitis, intraventricular hemorrhage and mortality.

The distribution of variables will be assessed with Shapiro Wilk test, normally distributed data will be compared with t test or Chi squared test and those with abnormal distribution with Mann-Whitney U test or Fisher exact test. The risk of hyponatremia and hypernatremia will be expressed using relative risk.

The change of serum sodium, creatinine, chloride, sodium bicarbonate, glucose levels and weight will be evaluated using repeated measures ANOVA or Kruskal-Wallis test depending on data distribution.

Exploratory analysis will include sodium balance (according to sodium intake and urinary excretion), urine output and total fluid administration.

IBM SPSS Statistics (IBM Corp. Released in 2013. IBM Statistics for Windows, Version 21.0. Armonk NY: IBM Corp.) will be used for statistical analysis. A p-value <0.05 will be considered statistically significant.

Definitions:

Hyponatremia: Serum sodium <130mEq/L

Hypernatremia: Serum sodium >150mEq/L

Change in serum sodium: The difference between serum sodium (at 48 and 72hrs) and initial serum sodium.

Weight change: The difference between weight (at 24, 48 and 72hrs) and birth weight.

Sepsis: Positive blood culture and/or 5 days of continuous antimicrobial therapy.

Necrotizing enterocolitis: Necrotizing enterocolitis according to Bell staging (II or grater).

Intraventricular hemorrhage: Bleeding into the brain's ventricular system (intracranial ultrasound).

Mortality: Death during hospitalization.

References

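### Weight change is defined as an absolute difference from birth weight, with no lower limit of gestation or weight and no birth-weight adjustment, so objective 4 cannot be read as degree of weight loss

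*Combined protocol and SAP*

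**What the plan says.** Objective 4 reads: "Assess the weight change in preterm newborns with early sodium intake and late sodium intake". The Definitions section fixes the endpoint as "Weight change: The difference between weight (at 24, 48 and 72hrs) and birth weight". It gives no unit, no percentage and no division by birth weight.

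The eligibility criteria are "Preterm infants <35 weeks of gestation" and "Less than 24 hours of life". There is no lower limit of gestation and no birth-weight limit in either direction.

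Under Study design and statistical analysis, "The eligible patients will be simple randomized in two groups", with no stratification. Birth weight is collected ("At admission, gestational age and sex and birth weight will be recorded") but has no role beyond the subtraction. Weight change is among the outcomes compared between groups over 72 hours, and the closing part of the sentence on longitudinal measures says that "glucose levels and weight will be evaluated using repeated measures ANOVA or Kruskal-Wallis test depending on data distribution". No covariate is named.

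**The concern.** A subtraction treats a given loss as the same event at every body size. In a population bounded only above, the same proportional loss becomes a small number in a small infant and a large one in a big infant. The plan itself sets sodium intake per kg in both arms, but does not express the body-weight outcome relative to body weight.

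What is at stake is mainly interpretation. A mean absolute difference between arms describes total weight lost, with larger infants counting for more. It does not say how severe the loss was relative to size, and it says least about the smallest infants. Precision may also suffer, but by how much, and even in which direction, depends on facts that the documents do not give.

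**Working it through.** The plan states no sample size, SD or expected weight change, so it has no figure to reproduce. Every distribution below is an assumption. Grams are used for illustration; any absolute unit behaves the same way.

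**1. Scale (arithmetic only; the two birth weights are illustrative).**
- 8% x 700 g = 56 g; 8% x 2200 g = 176 g; ratio 176/56 = 3.1.
- 100/700 = 14%; 100/2200 = 4.5%.

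**2. Weighting by size.** Suppose the sodium effect is a constant number of percentage points. Each infant then contributes to the mean absolute effect in proportion to birth weight. With roughly normal birth weight (mean m, SD s), the heaviest third averages about m + 1.09s, so its share is (1/3)(1 + 1.09 s/m).
- 1500/300 g: (1/3)(1 + 0.218) = 41%
- 1500/450 g: (1/3)(1 + 0.327) = 44%
- 1300/450 g: (1/3)(1 + 0.377) = 46%
- 1500/600 g: (1/3)(1 + 0.436) = 48%, or 47% by simulation with birth weight limited to 500-2600 g

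An even share is 33%. The lightest third supplies about 19-26%.

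**3. Precision if percent loss does not depend on size.** Assumed: birth weight mean 1400-1700 g, SD 350-500 g, limited to 500-2800 g in simulation; mean change -6% in one arm and -4% in the other (a 2-point effect); SD σ of 3-4 points. Averaged over the arms, the squared mean is (36 + 16)/2 = 26. With pooled variance, and ignoring the limits on birth weight:

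information ratio (absolute/percent) = 1 / [1 + (s/m)² (1 + 26/σ²)]

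- 1500/450, σ = 4: 1/(1 + 0.09 x 2.625) = 0.81
- 1400/500, σ = 3: 1/(1 + 0.1276 x 3.889) = 0.67 (0.68 by simulation)
- 1400/350, σ = 4: 1/(1 + 0.0625 x 2.625) = 0.86

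The range is about 68-86%. It reaches 90% where birth-weight SD is smallest relative to the mean: 1700/350, σ = 4 gives 1/(1 + 0.0424 x 2.625) = 0.90.

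**4. Precision if smaller infants lose a larger percentage.** Same inputs, with percent loss rising by k points for each kg below the mean birth weight, by simulation:

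| k (points per kg) | information, absolute/percent |
|---|---|
| 0 | about 68-86% |
| 2 | about 91-98% |
| 4 | over 100% |

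**5. Chance imbalance in birth weight.** Near the mean, the absolute change moves with birth weight at a rate of (mean percent change + k x m). For a 150 g imbalance at m = 1.5 kg in the arm averaging -6%:
- k = 0: 150 x 6% = 9 g
- k = 2: 150 x (6% - 3%) = 4.5 g
- k = 4: 150 x (6% - 6%) = 0 g

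The assumed true effect is 2% x 1500 = 30 g.

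**6. Adjustment.** With k = 0, adding birth weight linearly to the absolute analysis brings it to about 89-96% of the unadjusted percent-scale information. When both scales are adjusted for birth weight, percent was the more precise in every scenario run (k = 0, 2 and 4), given an effect constant in percentage points.

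**The case against.** The strongest objection is that any precision claim rests on percent loss being unrelated to body size. The documents do not say so and give no weight-loss data. Step 4 shows that a moderate gradient removes the disadvantage and a steeper one reverses it. This stands. A reader might infer that the absolute scale certainly wastes a quantifiable part of the sample, or that a birth-weight imbalance would create a false difference of about 9 g. Neither is supported: both figures belong to the no-gradient case, and the 150 g imbalance is itself arbitrary. Randomization equalizes birth weight in expectation, so an imbalance is noise rather than bias.

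Second, much of any precision loss comes from having no birth-weight covariate, not from the scale. This also stands, and the fix includes the covariate. Adjustment alone would still leave an estimate in absolute units that gives larger infants more weight.

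Third, the plan never says grams, so this could be simple silence about units. That is fair as far as the unit goes. The definition is nevertheless a difference, and nothing elsewhere relates it to birth weight.

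Fourth, the consequence is limited. The hypothesis concerns hyponatremia, and percent change can be derived from data already held. That limits the severity, but a scale chosen at analysis is weaker than one fixed in the definition.

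**Conclusion.** The point holds as a defect of scale and interpretation in objective 4. By arithmetic alone, equal proportional losses differ about three-fold between a 700 g and a 2200 g infant, and eligibility has no lower limit to exclude such a spread. The actual spread is not given.

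Larger infants are over-weighted: about 41-47% of the mean effect comes from the heaviest third, under the assumed distributions and an effect proportional to weight. A reader might infer that they dominate the result; these shares, against an even 33%, do not go that far.

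The effect on precision is undetermined. The absolute scale is worse without a size gradient, close to equal at 2 points per kg and better at 4 points per kg. The case for percent therefore rests on interpretability and, once birth weight is in the model, on its precision under an effect constant in percentage points. No bias is shown, and objectives 1 and 2 are untouched. The change should be made, but the trial's main question does not depend on it.

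**What to change.** Replace the definition with: Weight change (%) = 100 x (weight at 24, 48 or 72 h - birth weight) / birth weight; negative = loss.

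Use this for the objective 4 comparison, with birth weight as a covariate in the repeated-measures model. The Kruskal-Wallis alternative cannot carry a covariate; if it is used, apply it to the percent change and say that it is unadjusted. Report the absolute change by arm, with its unit, as a descriptive table.

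The cost is one line in the definitions and one in the analysis text. Birth weight and daily weights are already collected, so conduct does not change. The downside is that the absolute change becomes descriptive only.

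### If study sodium starts at 24 hours of life, the 24 h weight change from birth is pre-treatment, and the 48 and 72 h changes carry the same first-day loss as noise

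*Combined protocol and SAP*

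**What the plan says.** The Definitions give the weight outcome as "Weight change: The difference between weight (at 24, 48 and 72hrs) and birth weight". The line before it treats serum sodium differently, with no 24 h change value: "Change in serum sodium: The difference between serum sodium (at 48 and 72hrs) and initial serum sodium".

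On when study sodium starts, the Introduction says "Infants receive at 24 hours of life; sodium (5mEq/kg/day) versus less than 1mEq/kg/day", and the hypothesis agrees: "early (24 hours of life) sodium supplementation (5mEq/kg/day) prevents the develop of hyponatremia in preterm infants". The arm description under Study design and statistical analysis says "Sodium administration, enteral and/or parenteral of 5mEq/kg/day starting on day of life one", which gives no hour, and the age criterion for enrolment is "Less than 24 hours of life".

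Birth weight is recorded at admission, and after that "Weight will be evaluated every 24 hours for 3 days". Weight is analysed by repeated measures ANOVA or Kruskal-Wallis. The plan names no decisive term or contrast, no baseline covariate, and no weight at the start of study sodium. Comparing weight change between the arms is objective 4 of five.

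**The concern.** An outcome meant to show a treatment effect should be counted from a point at or near the start of treatment. If study sodium starts at 24 hours, the arms have not yet been treated differently when the 24 h weight is taken. The birth-to-24 h change then belongs among the baseline data, and it is also a component of the 48 and 72 h changes. Stating the change as a percentage, or adjusting for birth weight alone, does not remove it, because the unwanted part is the first-day loss itself.

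What is at stake is the sensitivity of objective 4. A real difference in weight after 24 hours is harder to detect in a single-time comparison, or in an average over the three times, when between-infant variation from before treatment is left in.

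**Working it through.** **Inputs.** From the documents: the three weight-change times, the birth reference, the 24-hourly weighing, and significance at 0.05 (taken as two-sided). The documents give no sample size, effect size, SD or correlation for weight, so there is no planned figure to reproduce. Every size below rests on assumptions, in percent of birth weight, and on sodium starting at 24 h.

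**Step 1: the identity.** With W0, W24, W48 and W72 the weights at birth and at each time, W72 − W0 = (W24 − W0) + (W72 − W24), and likewise for 48 h. The first bracket is pre-treatment on a 24 h start.

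**Step 2: bias.** The first bracket has the same expectation in both randomized arms. In 20,000 simulated trials (30 per arm, true later difference 2, first-day and later SDs both 3, uncorrelated), the mean estimate was 1.98 (SE 1.09) from birth and 1.99 (SE 0.78) from the 24 h weight. The 24 h change itself averaged −0.01. The birth reference cost precision and added no bias.

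**Step 3: the 72 h comparison alone.** Assume independent daily changes, first-day SD s1 and SD 2.8 on each later day. The variance ratio, birth reference over 24 h reference, is (s1² + 2 × 2.8²) / (2 × 2.8²) = (s1² + 15.68) / 15.68.

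- s1 = 2: 19.68 / 15.68 = 1.26
- s1 = 3: 24.68 / 15.68 = 1.57
- s1 = 4: 31.68 / 15.68 = 2.02

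These are also the ratios of infants needed for equal power.

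**Step 4: the average over times (group main effect).** Let the arm difference be 0, d/2 and d at 24, 48 and 72 h.

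- Three changes from birth: effect 0.50d, variance s1² + (4/9 + 1/9) × 7.84 = s1² + 4.36.
- Two changes from the 24 h weight: effect 0.75d, variance (1 + 1/4) × 7.84 = 9.80.

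The ratio of infants needed is (0.75² / 9.80) × (s1² + 4.36) / 0.50² = 1.92, 3.07 and 4.67 for s1 = 2, 3 and 4. For illustration, with 50 per arm and d = 2, power is 41%, 28% and 20%, against 67% from the 24 h weight.

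The smaller multiple of d is not in itself a loss. With s1 = 0 the ratio is 1.00, and with s1 = 1 it is 1.23. The loss comes from the first-day variation.

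**Step 5: the group-by-time interaction.** Subtracting any constant within an infant, whether birth weight or 24 h weight, leaves this term unchanged when all three times are analysed. Under the assumptions of step 4, simulation gives it about 69% power (Greenhouse-Geisser corrected) at every s1 from 2 to 4.

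**Step 6: correlation.** Let q be the first-day SD over the SD of the total later change, and r their correlation. The 72 h variance ratio, birth over 24 h reference, is q² + 1 + 2rq.

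- At r = −0.3, with first-day SD 2-4 and later SD 3-5, it runs from 0.92 (0.16 + 1 − 0.24) to 1.98.
- At r = −0.5 and q = 0.5 it is 0.25 + 1 − 0.50 = 0.75, so plain subtraction of the 24 h weight would lose precision.
- At r = −0.3 the step 4 ratios fall to 1.37, 2.25 and 3.58. At r = −0.5 and s1 = 2 the ratio is 1.01.

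**Step 7: first-day change as a covariate.** The later variance becomes (1 − r²) times its unadjusted value, so the ratio, birth reference over adjusted, is (q² + 1 + 2rq) / (1 − r²) = 1 + (q + r)² / (1 − r²). Apart from the one degree of freedom spent, this cannot fall below 1. Over first-day SD 2-4, later SD 3-5 and r from −0.5 to 0.3 it runs from 1.00 to 3.93.

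**The case against.** The strongest objection is that the start time is not settled. The arm description and the age limit for enrolment allow sodium to begin before 24 hours. The 24 h weight would then be post-treatment, using it as baseline would subtract treatment effect, and no weight at the start of sodium is scheduled. This stands, and it makes the whole point conditional. A reader might infer that the 24 h value cannot carry any treatment effect. The documents do not support that without the condition.

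Second, a reader might infer bias in the 48 and 72 h comparisons. Randomization rules that out in expectation. What remains is added variance and, under simple randomization, chance imbalance in first-day loss.

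Third, the larger ratios apply only to the group main effect. The plan does not say which ANOVA term decides, and the interaction keeps its power. So the documents do not show that the planned ANOVA as a whole would miss a real effect. Equally, nothing in the plan makes the interaction the deciding test, and single-time comparisons do depend on the reference.

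Fourth, it is tempting to say that the sodium and weight definitions use different origins. The initial serum sodium has no stated hour and could be an admission sample. Only the difference in outcome times is established.

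Finally, change from birth weight is a legitimate and familiar clinical figure, and objective 4 is fourth of five. That limits the weight of the point but does not answer it.

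**Conclusion.** The point holds on condition that study sodium starts at 24 hours of life. The 24 h weight change is then a baseline quantity listed as an outcome, and first-day loss usually adds noise to the single-time comparisons at 48 and 72 h and to the group main effect. There is no bias, and the interaction over all three times is untouched.

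The true size cannot be known from the documents. The inflation in infants needed (1.3-2.0 times at 72 h, 1.9-4.7 times for the three-time average) assumes independent daily changes, a later daily SD of 2.8% and a first-day SD of 2-4%. The three-time figure also assumes an arm difference that is half as large at 48 h as at 72 h. Negative correlation reduces the inflation, and at 72 h can reverse it. This is a modest efficiency and clarity issue that existing measurements can address.

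**What to change.** First, reconcile the Introduction and hypothesis with the arm descriptions on when study sodium starts, and state the hour.

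If it is 24 h:

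- compare arms on weight at 48 and 72 h with the 24 h weight as baseline, preferably as a covariate (ANCOVA, with birth weight also in the model) rather than only as a subtracted reference;
- report the birth-to-24 h change as a baseline characteristic;
- keep change from birth as a descriptive result.

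If sodium can start before 24 h, the 24 h weight must not serve as baseline. Keep the birth reference and adjust for birth weight.

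The cost is a few lines in the Definitions and the analysis text. Neither branch needs a new measurement, because weight is already taken every 24 hours. The small downside, if the start is 24 h, is that the familiar change-from-birth figure becomes descriptive.

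### The sepsis outcome mixes culture-proven sepsis with any 5-day antimicrobial course, whatever its indication or start date, so the comparison between arms can be diluted or biased in either direction

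*Combined protocol and SAP*

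**What the plan says.** The Definitions section of the combined protocol and SAP reads "Sepsis: Positive blood culture and/or 5 days of continuous antimicrobial therapy". The wording makes each part sufficient by itself. The antimicrobial part names no indication, clinical sign, laboratory finding or start date.

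The only statement on timing is in Study design and statistical analysis: "The patients will be following through hospital stay to record the development of sepsis, necrotizing enterocolitis, intraventricular hemorrhage and mortality". Infants enter at "Less than 24 hours of life". The exclusion criteria cover four groups of malformations and do not mention infection or antimicrobial treatment at entry. NEC is a separate outcome with its own definition, Bell stage II or above.

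Sepsis is one of four complications in objective 5, the last of five: "Assess the development of complications (sepsis, necrotizing enterocolitis, intraventricular hemorrhage, mortality) in preterm newborns with early sodium intake and late sodium intake". The hypothesis concerns a different outcome, namely that "sodium supplementation (5mEq/kg/day) prevents the develop of hyponatremia in preterm infants". The document describes no masking, and it gives no expected sepsis rate, antimicrobial policy or sample size.

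**The concern.** Applied literally, the rule counts two kinds of infant who may not have the complication that objective 5 is meant to compare.

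- **Courses begun before randomisation.** A course started around birth and continued to day 5 counts as sepsis, although the allocated sodium cannot have caused the condition that prompted it.
- **Courses given for NEC.** Five days of antimicrobials for NEC also make the infant a sepsis case. Any difference between arms in NEC then reappears under sepsis.

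The length of a course is also a ward decision. With no masking described, it could be influenced by knowledge of the arm.

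The sepsis comparison is part of the safety picture for the higher sodium intake. With this definition, neither a difference nor the absence of one could be read with confidence.

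**Working it through.** The plan states no figure for sepsis, so there is none to reproduce. What follows is an illustration, and every risk in it is assumed. The plan promises a relative risk (RR) only for hyponatremia and hypernatremia; I use it here as a convenient scale.

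**Set-up.** Let p be the true sepsis risk in an arm and f the share of its non-septic infants who meet the 5-day rule. Assume that every true case is captured. Then

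observed risk = p + (1 − p) × f.

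For sample size, assume two-sided alpha 0.05 (the plan gives 0.05 without sidedness), 80% power and equal arms:

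n per arm = 7.849 × [p1(1 − p1) + p2(1 − p2)] / (p1 − p2)², where 7.849 = (1.960 + 0.8416)².

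**Case 1: f equal in both arms, true risks 10% and 20%.** The risk difference shrinks by exactly the factor (1 − f).

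| f | Observed risks | Difference (points) | RR | n per arm |
|---|---|---|---|---|
| 0 | 10% vs 20% | 10 | 2.00 | 7.849 × 0.2500 / 0.0100 = 196 |
| 0.1 | 19% vs 28% | 9 | 1.47 | 7.849 × 0.3555 / 0.0081 = 344 |
| 0.3 | 37% vs 44% | 7 | 1.19 | 7.849 × 0.4795 / 0.0049 = 768 |
| 0.5 | 55% vs 60% | 5 | 1.09 | 7.849 × 0.4875 / 0.0025 = 1,531 |

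**Case 2: f differs by arm, same true risks.** RR is the higher-risk arm over the lower-risk arm.

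- f = 0.30 in the higher-risk arm and 0.10 in the lower: 0.20 + 0.80 × 0.30 = 44% against 0.10 + 0.90 × 0.10 = 19%. The difference grows to 25 points and RR rises to 44/19 = 2.32, away from no effect on both scales.
- f = 0.30 and 0.20: 44% against 28%. The difference grows to 16 points while RR falls to 1.57.
- f = 0.20 and 0.30: 36% against 37%. The true difference vanishes and slightly reverses (RR 0.97).

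**Case 3: no true effect, 15% in both arms.** With f = 0.30 in one arm and 0.20 in the other, the observed risks are 0.15 + 0.85 × 0.30 = 40.5% and 0.15 + 0.85 × 0.20 = 32%. A spurious RR of 1.27 appears, or 0.79 if the arms are swapped.

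**The case against.** Several points on the other side stand.

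- **Not simply antibiotic use.** A reader might infer that the outcome only measures antimicrobial use. The document does not support that: a positive culture also qualifies alone, so this is a composite, and the share that comes from antimicrobials alone cannot be known from the plan.
- **Not always dilution.** A reader might also infer that the rule always pulls a difference towards no effect. Case 1 needs equal false-positive rates. That is plausible for courses begun before randomisation. It is not assured for later courses, nor for NEC courses if NEC itself differs by arm.
- **No total is double-counted.** One illness can enter both sepsis and NEC, but the plan forms no sum or composite of complications. What remains is the carry-over of an NEC difference into sepsis.
- **Early deaths are not lost.** A culture-negative infant who dies on antimicrobials before day 5 is sepsis-free under the rule but counts under mortality.
- **New events are hinted at.** Recording the development of sepsis suggests new onset. No rule enforces this, however, and the gap affects the culture part as well.
- **The figures are assumed.** With no planned sample size, the numbers per arm show only relative inflation.

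Replacing the outcome with culture-positive sepsis alone would also have a price. If culture detected half of true cases in each arm (an assumption), the risks would be 5% and 10%. RR would stay at 2.0, but n would be 7.849 × (0.0475 + 0.0900) / 0.0025 = about 432 per arm, more than the 344 at f = 0.1. That argues for two reported lines, not for dropping the antimicrobial part.

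**Conclusion.** The concern holds in this form: the definition combines culture-proven sepsis with 5-day antimicrobial courses of any indication and any start date. It therefore admits courses begun before randomisation and courses given for NEC. This follows from the stated rule and needs no assumed figure.

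The size does rest on assumptions. With true risks of 10% and 20%, full capture of true cases and equal false-positive rates of 10% to 50%, RR falls from 2.0 to between 1.47 and 1.09. If the rates differ by arm, the bias can exaggerate, hide or reverse a difference, or create one. The document does not allow a choice between these directions.

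The consequence is confined to one complication under objective 5. The definition is worth correcting because the change is cheap, but it does not threaten the trial's hypothesis.

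**What to change.** Count a sepsis event only if its onset is after randomisation, by the same rule in both arms. Randomisation is a safer anchor than the start of study sodium: the comparison arm is allocated less than 1 mEq/kg/day, which may be none, so a sodium start time may not exist there. Date onset by when the culture was drawn or the antimicrobial course began.

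Report two lines by arm:

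- (a) culture-positive sepsis;
- (b) culture-negative antimicrobial courses of 5 days or more that started after randomisation and were not given for NEC.

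State that culture-negative infants who die on antimicrobials before day 5 are counted under mortality, and list them by arm alongside line (b).

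The cost is the revised definition plus culture date, antimicrobial start date and indication from the chart; no new procedure is needed. Each line will have fewer events than the present combined outcome. Line (b) will still depend on ward decisions about course length, but it will no longer be mixed with proven infection.
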